7.2.3.2 Events of Clinical Interest

Selected non-serious and serious adverse events are also known as Events of Clinical Interest (ECI) and must be reported within 24 hours to the Sponsor and within 2 working days to Merck Global Safety. (Attn: Worldwide Product Safety; [contact]).

For the time period beginning when the consent form is signed until treatment allocation/randomization, any ECI, or follow up to an ECI, that occurs to any subject must be reported within 24 hours to the Sponsor and within 2 working days to Merck Global Safety if it causes the subject to be excluded from the trial, or is the result of a protocol-specified intervention, including but not limited to washout or discontinuation of usual therapy, diet, placebo treatment or a procedure.

For the time period beginning at treatment allocation/randomization through 90 days following cessation of treatment, or 30 days following cessation of treatment if the subject initiates new anticancer therapy, whichever is earlier, any ECI, or follow up to an ECI, whether or not related to Merck product, must be reported within 24 hours to the Sponsor and within 24 hours to Merck Global Safety.

Events of clinical interest for this trial include:

- a.** an overdose of Merck product, as defined in Section 7.2.1 - Definition of an Overdose for This Protocol and Reporting of Overdose to the Sponsor, that is not associated with clinical symptoms or abnormal laboratory results.
- b.** 2. an elevated AST or ALT lab value that is greater than or equal to 3X the upper limit of normal and an elevated total bilirubin lab value that is greater than or equal to 2X the upper limit of normal and, at the same time, an alkaline phosphatase lab value that is less than 2X the upper limit of normal, as determined by way of protocol-specified laboratory testing or unscheduled laboratory testing.*

***Note:** These criteria are based upon available regulatory guidance documents. The purpose of the criteria is to specify a threshold of abnormal hepatic tests that may require an additional evaluation for an underlying etiology.

7.2.3.3 Protocol-Specific Exceptions to Serious Adverse Event Reporting

Efficacy endpoints as outlined in this section will not be reported to Merck as described in Section 7.2.3.- Immediate Reporting of Adverse Events to the Sponsor and to Merck, unless there is evidence suggesting a causal relationship between the drug and the event. Any such event will be submitted to the Sponsor within 24 hours and to Merck Global Safety within 2 working days either by electronic or paper media.

Specifically, the suspected/actual events covered in this exception include any event that is disease progression of the cancer under study.

The Sponsor will monitor unblinded aggregated efficacy endpoint events and safety data to ensure the safety of the subjects in the trial. Any suspected endpoint which upon review is not progression of the cancer under study will be forwarded to Merck Global Safety as a SAE within 2 working days of determination that the event is not progression of the cancer under study

Hospitalization related to convenience (e.g.transportation issues etc.) will not be considered a SAE.

7.2.4 Evaluating Adverse Events

An investigator who is a qualified physician will evaluate all adverse events according to the NCI Common Terminology for Adverse Events (CTCAE), version 4.0. Any adverse event which changes CTCAE grade over the course of a given episode will have each change of grade recorded on the adverse event case report forms/worksheets.

All adverse events regardless of CTCAE grade must also be evaluated for seriousness.

Table 6 Evaluating Adverse Events	
An investigator who is a qualified physician, will evaluate all adverse events as to:	
V4.0 CTCAE Grading	
Grade 1	Mild; asymptomatic or mild symptoms; clinical or diagnostic observations only; intervention not indicated

Grade 2	Moderate; minimal, local or noninvasive intervention indicated; limiting age-appropriate instrumental ADL.
Grade 3	Severe or medically significant but not immediately life-threatening; hospitalization or prolongation of hospitalization indicated; disabling; limiting self-care ADL.
Grade 4	Life threatening consequences; urgent intervention indicated.
Grade 5	Death related to AE
Seriousness	A serious adverse event is any adverse event occurring at any dose or during any use of Merck or Oncologie product that:
†Results in death; or	
†Is life threatening;	or places the subject, in the view of the investigator, at immediate risk of death from the event as it occurred

Note: This does not include an adverse event that, had it occurred in a more severe form, might have caused death; or
	
†Results in a persistent or significant disability/incapacity	substantial disruption of one's ability to conduct normal life functions; or
†Results in or prolongs an existing inpatient hospitalization	hospitalization is defined as an inpatient admission, regardless of length of stay, even if the hospitalization is a precautionary measure for continued observation.

Note: Hospitalization for an elective procedure to treat a pre-existing condition that has not worsened is not a serious adverse event.
	

Note: A pre-existing condition is a clinical condition that is diagnosed prior to the use of a Merck product and is documented in the patient's medical history; or
	
†Is a congenital anomaly/birth defect	(in offspring of subject taking the product regardless of time to diagnosis); or

Is a new cancer	(that is not a condition of the study) (although not serious per ICH definition, is reportable to the PI within 24 hours and to Merck and Oncologie within 2 working days to meet certain local requirements); or
Is an overdose (whether accidental or intentional).	Any adverse event associated with an overdose is considered a serious adverse event for collection purposes. An overdose that is not associated with an adverse event is considered a non-serious event of clinical interest and must be reported within 24 hours to the PI and to Merck and Oncologie within 2 working days.
Other important medical events	that may not result in death, not be life threatening, or not require hospitalization may be considered a serious adverse event when, based upon appropriate medical judgment, the event may jeopardize the subject and may require medical or surgical intervention to prevent one of the outcomes listed previously (designated above by a †).
Duration Record	the start and stop dates of the adverse event. If less than 1 day, indicate the appropriate length of time and units
Action Taken	Did the adverse event cause Merck or Oncologie product to be discontinued?

Relationship to Merck/Oncologie Product	Did Merck or Oncologie product cause the adverse event? The determination of the likelihood that the Merck or Oncologie product caused the adverse event will be provided by an investigator who is a qualified physician. The investigator's signed/dated initials on the source document or worksheet that supports the causality noted on the AE form, ensures that a medically qualified assessment of causality was done. This initialed document must be retained for the required regulatory time frame. The criteria below are intended as reference guidelines to assist the investigator in assessing the likelihood of a relationship between the test drug and the adverse event based upon the available information.
The following components are to be used to assess the relationship between Merck product and the AE; the greater the correlation with the components and their respective elements (in number and/or intensity), the more likely Merck product caused the adverse event (AE):	
Exposure	Is there evidence that the subject was actually exposed to Merck or Oncologie product such as: reliable history, acceptable compliance assessment (pill count, diary, etc.), expected pharmacologic effect, or measurement of drug/metabolite in bodily specimen?
Time Course	Did the AE follow in a reasonable temporal sequence from administration of Merck or Oncologie product?
Time of Onset	Is the time of onset of the AE compatible with a drug-induced effect (applies to trials with investigational medicinal product)?

Likely Cause	Is the AE not reasonably explained by another etiology such as underlying disease, other drug(s)/vaccine(s), or other host or environmental factors
Relationship	The following components are to be used to assess the relationship between the test drug and the AE: (continued)
	to Merck or Oncologie Product
Dechallenge	Was Merck or Oncologie product discontinued or dose/exposure/frequency reduced?
If yes,	did the AE resolve or improve?
If yes,	this is a positive dechallenge.
If no,	this is a negative dechallenge.

Note: This criterion is not applicable if:
 
 1) the AE resulted in death or permanent disability; 2) the AE resolved/improved despite continuation of the Sponsor's product; or 3) the trial is a single-dose drug trial); or 4) Sponsor's product(s) is/are only used one time. 	
Rechallenge	Was the subject re-exposed to Merck or Oncologie product in this study?
If yes,	did the AE recur or worsen?
If yes,	this is a positive rechallenge.
If no,	this is a negative rechallenge.

Note: This criterion is not applicable if:
 
 1) the initial AE resulted in death or permanent disability, or 2) the trial is a single-dose drug trial); or 3) Sponsor's product(s) is/are used only one time. 	

NOTE: IF A RECHALLENGE IS PLANNED FOR AN ADVERSE EVENT WHICH WAS SERIOUS AND WHICH MAY HAVE BEEN CAUSED BY MERCK PRODUCT, OR IF REEXPOSURE TO MERCK PRODUCT POSES ADDITIONAL POTENTIAL SIGNIFICANT RISK TO THE SUBJECT, THEN THE RECHALLENGE MUST BE APPROVED IN ADVANCE BY THE SPONSOR AS PER DOSE MODIFICATION GUIDELINES IN THE PROTOCOL.
	
Consistency with Trial Treatment Profile	Is the clinical/pathological presentation of the AE consistent with previous knowledge regarding Merck product or drug class pharmacology or toxicology?

Note: The assessment of relationship will be reported on the case report forms /worksheets by an investigator who is a qualified physician according to his/her best clinical judgment, including consideration of the above elements.
	

Record one of the following:
 
Use the following scale of criteria as guidance (not all criteria must be present to be indicative of Merck product relationship).
	
Yes, there is a reasonable possibility of Merck product relationship.	
There is evidence of exposure to Merck or Oncologie product.
 
The temporal sequence of the AE onset relative to the administration of Merck product is reasonable.
 
The AE is more likely explained by Merck product than by another cause.

No, there is not a reasonable possibility of Merck product relationship.	Subject did not receive the Merck or Oncologie product OR temporal sequence of the AE onset relative to administration of Merck or Oncologie product is not reasonable OR the AE is more likely explained by another cause than the Merck or Oncologie product. (Also, entered for a subject with overdose without an associated AE.)
---	--

8. LABORATORY EVALUATIONS

8.1 Efficacy Measures

Patients will be re-staged every 3 cycles and treatment will continue until progression, or significant toxicity up to 24 months. Staging assessments will include cross-section imaging with either MRI head and neck or CT head and neck with contrast, and CT chest/abdomen with contrast.

8.2 The Following Laboratory Parameters Will Be Assessed:

Hematology: complete blood count (red blood cell count, white blood cell count, hemoglobin, hematocrit, mean corpuscular volume, mean corpuscular hemoglobin, and mean corpuscular hemoglobin concentration) with differentials, and platelets,

Chemistry: AST, ALT, gamma-glutamyl transpeptidase, alkaline phosphatase, lactate dehydrogenase, creatinine, blood urea nitrogen, serum bilirubin (serum total and direct bilirubin at screening, direct bilirubin subsequently only if serum total bilirubin is elevated), total protein, albumin, glucose, uric acid, magnesium, phosphate, amylase, lipase, electrolytes (sodium, potassium, chloride, calcium, and bicarbonate), thyroid function tests (thyroid stimulating hormone [TSH] reflex to free triiodothyronine and free thyronine if abnormal TSH result).

Urinalysis: specific gravity, pH, dipstick for blood, glucose, protein, and microscopy for cells and casts.

Pregnancy testing for women of childbearing potential - See section 3.1.8

Other safety evaluations will be made based on regular vital signs assessments (heart rate, systolic and diastolic blood pressure, oxygenation at rest and walking, weight) and physical examinations.

8.3 Correlative Studies - Please see lab manual for full details regarding collection and processing.

Exploratory correlative studies are planned in order to determine biomarkers that may be related to response to therapy. Blood will be collected at baseline, during each cycle and at the end of the study. The blood samples from the baseline, cycles 2, 4, and the end of the study will be used for DNA extraction and biomarker discovery analyses (mutation- and methylation-specific). The blood samples at cycles 1 and 3 will be preserved in case of any issues or with blood samples at cycles 2 and 4. Fresh biopsy tissue will be obtained at the baseline and if feasible at the end of the study. Fresh biopsy tissue will be used for DNA and RNA extraction. The following correlative studies will be performed:

- 8.3.1** *H&E staining will be performed on each tumor samples to define the tumor histology. This will be performed at the University of Maryland Pathology Department under the direction of [name].*
- 8.3.2** *Immunohistochemical analysis of PD-L1 protein expression will be performed on primary tumor samples at the baseline and the end of the study.*
- 8.3.3** *HPV status will be obtained as per clinical standard. If this data is available in the medical record repeat testing is not necessary.*
- 8.3.4** *The somatic genomic analysis will be performed using AmpliSeq platform on primary tumor tissues collected at the baseline and the end of the study, as well as on the blood samples collected at the baseline, cycles 2, 4, and the end of the study. DNA from plasma will be used for such AmpliSeq analysis. DNA from lymphocytes collected at the baseline will be used as a somatic control for mutation detection. Tumor and blood samples will be compared at the baseline and the end of the study to define the blood-based detection specificity and sensitivity. Overall, 7 samples per patient will be used for AmpliSeq analysis.*
- 8.3.5** *DNA methylation analysis of primary samples will be performed on tumor samples at the baseline and the end of the study using DNA methylation array 850K (Illumina) to define DNA methylation-based biomarkers. All DNA samples will be bisulfite-converted before the analysis. For this reason, the extracted DNA from n=15 normal mucosa of non-cancer patients matched by the age, gender and smoking status (available from Otolaryngology tissue bank) will be used as non-cancer controls. The panel of 10 hypermethylated DNA sites (including 4 well-characterized and 6 patient-unique signals) for each patient will be developed for each patient.*

8.3.6 *Ten hypermethylated DNA sites (developed for each patient) will be used for the design of droplet digital PCR (ddPCR) primers and probes assays. Plasma DNA at the baseline, cycles 2, 4, and the end of the study will be used as a template for ddPCR. All DNA samples will be bisulfite-converted before the analysis. The sensitivity and specificity of the developed ddPCR assay, as well as their ability to trace the treatment response, will be evaluated on this step.*

8.3.7 *Gene expression analysis landscape of tumors tissues before and after treatment will be evaluated on the primary samples at the baseline and the end of the study using low-throughput RNA-Seq analysis. For this reason, the extracted RNA from n=15 normal mucosa of non-cancer patients matched by the age, gender and smoking status (available from Otolaryngology tissue bank) will be used as non-cancer controls. Pathway analysis will be performed for each patient using the panel of differentially expressed genes relative to controls. This will allow defining the treatment response on the gene expression level. The gene expression will also be correlated with DNA methylation landscape to evaluate which of the cancer-related changes are triggered by epigenetic changes common for cancers.*

8.3.8 *The analysis of immune cell infiltration and cell repertoire will be performed for each sample using gene expression analysis of immune markers, as well as other immune-related and cell type-specific genes.*

8.3.9 *Immunohistochemical staining of immune markers (especially one detected on the RNA level) will be performed.*

9. STUDY CALENDAR

Baseline laboratory and exam evaluations are to be conducted within 10 days prior to start of protocol therapy. Scans and x-rays must be done \leq 4 weeks prior to the start of therapy. In the event that the patient's condition is deteriorating, laboratory evaluations should be repeated within 48 hours prior to initiation of the next cycle of therapy.

With the exception of screening evaluations, all time points on study have leeway of plus or minus 3 days.

	Pre-Study		3 week cycles (repeat)					EOS	Follow up
			Cycle 1	Cycle 2	Cycle 3	Cycle 4			
Pembrolizumab ¹			X	X	X	X			
Bavituximab ⁷			X	X	X	X			
Informed Consent	X								
History & Physical ²	X		X		X	X	X		
Concurrent Meds	X		X		X	X	X		
CBC and Chemistry ³	X		X			X			
Research Bloods ⁴	X		X		X	X	X	X	
β-HCG ⁸	X								
AE assessment	X		X		X	X	X		X
CT or MRI for Tumor Assessment ⁵	X ^{5*}						X ⁵		
Tumor Biopsy ⁶	X					X			
Review of medical records, telephone contact for recurrence-free and overall survival									Every 3 months up to 1 year

¹. 200 mg IV day 1 of each cycle up to 24 months while on study

². History to be collected only at baseline; physical, includes interval history, prior treatment and radiation exposure, vital signs, (heart rate, systolic and diastolic blood pressure, oxygenation at rest and walking, height, weight, and performance status. Height is only required at baseline.

³. Complete blood count and differential, and comprehensive metabolic panel, NOTE -TSH, Free T4 once every 4 weeks.

⁴. Amount is detailed in laboratory manual.

⁵. Tumor assessment includes radiologic assessment for RECISTv1.1 evaluation. Repeat radiologic assessment at week 9 and every 9 weeks thereafter while patient continues to receive study therapy.

⁶. Tumor biopsy to be obtained after cycle 4 if feasible. Archival tissue will be collected at baseline if pre-study biopsy is not feasible at the discretion of the PI.

⁷ Bavituximab is dosed weekly

⁸ See section 3.1.8

10. MEASUREMENT OF EFFECT

Antitumor Effect – Solid Tumors

On this study, planned radiologic evaluations will be performed at baseline (within 4 weeks prior to starting study therapy) and then every 3 cycles. Confirmatory scans should be obtained not less than 4 weeks following initial documentation of objective response, and will typically be obtained at the time of the next planned evaluation.

Response and progression will be evaluated in this study using the new international criteria proposed by the Immune-related Response Evaluation Criteria in Solid Tumors (irRECIST) guideline[Clin Cancer Res. 2009 Dec 1;15(23):7412-20] , Changes in the longest diameter (unidimensional measurement) of the tumor lesions and the shortest diameter in the case of malignant lymph nodes are used in the RECISTv1.1 criteria.

Accumulating evidence indicates that the emergence of objective responses to agents that activate anti-tumor immune responses may follow delayed kinetics of weeks or months, and can be preceded by initial apparent radiological progression, or the appearance of new lesions or some enlarging lesions while certain target lesions are regressing (“mixed response”). It is thus reasonable, in the absence of clinical deterioration, to continue to treat these subjects until radiologic progression is both confirmed and found to have worsened at a subsequent imaging evaluation. Evidence of PD will be based on a comparison with baseline (or nadir) scans, in which there is either an increase of 20% or more in the sum of the longest diameters (SLD) of target lesions taking as reference the smallest sum of the longest diameters (nadir) recorded since starting pembrolizumab/bavituximab treatment, and/or unequivocal progression of non-target lesions, with or without the development of 1 or more new lesions. PD should be confirmed by repeat scans at the next scheduled imaging evaluation 8 weeks later (but no sooner than 4 weeks).

Subjects with PD should be managed in the study as per Section 4.

10.1 Definitions

10.1.1 *Evaluable for toxicity*

All patients will be evaluable for toxicity from the time of their first treatment on protocol.

10.1.2 *Evaluable for objective response*

For each, only those patients who have measurable disease present at baseline, have received at least one cycle of therapy, and have had their disease re-evaluated will be considered evaluable for response. These patients will have their response classified according to the definitions stated below. (Note: Patients who exhibit objective disease progression prior to the end of the first cycle of either therapy will also be considered evaluable.)

10.1.3 *Evaluable Non-Target Disease Response*

Patients who have lesions present at baseline that are evaluable but do not meet the definitions of measurable disease, have received at least one cycle of therapy, and have had their disease re-evaluated will be considered evaluable for non-target disease. The response assessment is based on the presence, absence, or unequivocal progression of the lesions.

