11. STATISTICAL CONSIDERATIONS

The primary outcome of this study is overall response rate (CR+PR via RECIST 1.1). We will use a Simon's optimal 2-stage design with 80% power and 5% one-sided type-I error to compare the null hypothesis of ORR=5% vs. the alternative of ORR=20%. The first stage will enroll 10 patients, and if 1 or more responses are observed an additional 19 patients will be enrolled. If at least 4 responses are observed out of the 29 patients, the null hypothesis will be rejected

Safety Monitoring: We will monitor adverse events (AEs) throughout the study. If it appears that the risk of a serious AE is excessive, we will evaluate the treatment regimen and either modify the treatment plan or consider stopping the study. The risk of a serious AE (or DLT as defined above) is excessive if the risk is greater than 25%. Our stopping criterion corresponds to our determining that there is 75% or greater probability that the risk of a DLT exceeds 25%. Experience with single-agent anti-PD1 therapy suggests that the risk of a serious AE is between 15% and 20% but may be higher with the combination. We characterize this estimate with uncertainty using a beta distribution with parameters 2 and 8. This distribution has mean 0.2 and 90% probability that the risk is between 4% and 43%. The following table shows the stopping boundaries for safety monitoring.

Number of patients experiencing a DLT	4	5	6	7	8	9	10	11
Number of patients treated	4 - 6	7 - 9	10 - 13	14 - 17	18 - 20	21 - 24	25 - 27	28 - 29

Estimates of the operating characteristics for this stopping rule, as estimated from 5,000 simulations for each scenario, are as follows.

Risk of DLT	0.10	0.15	0.20	0.25	0.30	0.35	0.40	0.45	0.50
Chance of declaring the combination too toxic	1.2	4.8	14.2	31.2	51.7	71.5	86.9	94.9	98.3
Average sample size	28.8	28.1	26.6	24.0	20.8	17.2	13.7	11.1	9.1

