11.1 Data Analysis

We will summarize the response experience of the patients with percentages and confidence intervals. (We will not adjust for the interim analysis when computing the confidence intervals.) We will define overall survival as the time from the start of treatment until death from any cause. Patients who leave the study and whose survival status we cannot determine will be censored at the last date they were known to be alive. Progression-free survival will be the time from the start of treatment until disease progression or death from any cause. Patients who start non-protocol therapy in the

absence of disease progression will be considered to have progressed on the date the new therapy begins. If the patient is lost to follow up, the patient's time to progression will be censored at the last date they were known to be alive and disease free. Duration of response will be defined as the time from the first known response until disease progression, with death not related to disease censoring this endpoint. All failure-time endpoints will be analyzed with appropriate statistical methods for censored data. We will estimate the distributions of times until the events by the method of Kaplan and Meier. We will fit the proportional hazards model to learn about associations of patient or tumor characteristics with failure-time endpoints. Data displays will include summary statistics and confidence intervals.

Correlative analyses (e.g., laboratory correlates of response, such as PD-L1 expression, presence of TILs, and changes in immune markers) will be exploratory

Safety Analysis

All patients who receive any study treatment will be included in final summaries of safety data. Summaries of AEs and other safety parameters will be provided as appropriate. Summary tables for extent of exposure to study treatment will also be provided.

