11.2 Interim Analysis

The first stage will enroll 10 patients, and if 1 or more responses are observed an additional 19 patients will be enrolled. After the first 6 patients are accrued, the regimen will be evaluated for toxicity. If 2 or more patients experience a DLT, the study will be halted for excess toxicity.

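### No patient set is named for the reported ORR and its interval, and the only objective-response definition (10.1.2) can leave out treated early failures whom the Simon rule counts

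*Combined protocol and SAP*

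**What the plan says.** Section 11 makes ORR by RECIST 1.1 the primary outcome and tests 5% against 20% with a Simon two-stage design. The sizes are stated as patients enrolled: "The first stage will enroll 10 patients, and if 1 or more responses are observed an additional 19 patients will be enrolled" (11.2, and the same in 11). The final rule is "If at least 4 responses are observed out of the 29 patients, the null hypothesis will be rejected".

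Section 11.1 covers reporting: "We will summarize the response experience of the patients with percentages and confidence intervals". It names no set and does not refer to Section 10. For safety the same section does name one: "All patients who receive any study treatment will be included in final summaries of safety data".

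Section 10.1.2 defines who is evaluable for objective response: only patients with measurable disease at baseline who "have received at least one cycle of therapy, and have had their disease re-evaluated will be considered evaluable for response". A note adds one exception: "Patients who exhibit objective disease progression prior to the end of the first cycle of either therapy will also be considered evaluable". Section 10.1.3 concerns patients who "will be considered evaluable for non-target disease". It cannot supply the ORR set, because 3.1.4 makes measurable disease an entry criterion.

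The first on-study scan is at week 9 (Section 9, footnote 5). Section 4.3 requires no tumor assessment once treatment has stopped and uses the last on-protocol CT for response. The note in 10.4.4 gives a reporting category, symptomatic deterioration, to patients who stop because their general health declines without objective progression. It asks that progression still be documented afterwards where possible.

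**The concern.** Two denominators can be read from the plan, and nothing chooses between them. One is the 29 patients of the Simon rule. The other is the smaller group left after 10.1.2 is applied. Patients in the first group but not the second are those treated and never re-assessed, and in this setting they are mostly treatment failures: early deaths, early stops for toxicity, clinical decline before week 9. Under 3.1.1 everyone enters after progression on a checkpoint inhibitor and on platinum, so some early loss is plausible, although the documents give no expected number.

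A single-arm trial with ORR as its primary endpoint is read through that percentage and its interval. If the denominator is settled after responses are known, in an open-label study (5.2.4), the reported rate can be higher than the rate on which the decision was made, and the two would describe different patients.

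**Working it through.** **1. Reproduce the design.** Inputs from Section 11: p0 = 0.05, p1 = 0.20; 10 patients at stage 1, continue with 1 or more responses; 19 more; reject at 4 or more of 29.

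P(reject | p) = Σ over x = 1 to 10 of C(10,x) p^x (1−p)^(10−x) × P[Bin(19,p) ≥ max(0, 4−x)]

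- p = 0.05: 0.0468, within the stated 5%.
- p = 0.20: 0.8011, matching the stated 80%.
- Chance of stopping at stage 1 under the null: 0.95^10 = 0.599.

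The design is correct as a count among 10 and then 29 patients.

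**2. Who can fall outside 10.1.2.**

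| Treated patient | Inside 10.1.2? |
|---|---|
| At least one cycle and any re-evaluation | Yes |
| Objective progression before the end of cycle 1 | Yes, by the note |
| Unscheduled scan or caliper measurement before stopping, after at least one cycle | Yes, as a re-evaluation |
| Death before any re-assessment | No |
| Stop for toxicity before week 9, no scan | No |
| Clinical deterioration before week 9, no measurement | No; 10.4.4 gives a category but no denominator rule |

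Re-staging every 3 cycles of 21 days is 63 days, so week 9 is the first planned opportunity. The last-CT rule in 4.3 helps only patients who have an on-treatment CT.

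**3. Effect on the reported ORR.** With x responses and k of 29 patients left out, the estimate is x/(29−k) instead of x/29. The plan gives neither an interval level nor a method, so exact 95% Clopper-Pearson limits are assumed. The values of k are also assumed. For x = 4, the smallest positive result:

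| Left out | ORR | Exact 95% CI | Shift in estimate |
|---|---|---|---|
| 0 | 4/29 = 13.8% | 3.9 to 31.7 | – |
| 1 | 4/28 = 14.3% | 4.0 to 32.7 | +0.5 points |
| 3 | 4/26 = 15.4% | 4.4 to 34.9 | +1.6 points |
| 6 | 4/23 = 17.4% | 5.0 to 38.8 | +3.6 points |

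The interval on 29 is 31.7 − 3.9 = 27.8 points wide. The proportional inflation is 29/(29−k) for any x above 0; at k = 6 it is 29/23 = 1.26.

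**4. Effect on the decision.** An unassessed patient supplies no response whether or not he or she is in the denominator. The count x is therefore unchanged, and so is the rule of 4 or more among 29 enrolled. If stage 1 ends at 0 of 10, the ORR is 0% on any denominator and only the upper limit moves.

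**The case against.** The natural reading of 11.1, coming straight after Section 11, is that its patients are the same 29. Neither section cites 10.1.2, and 10.1.2 does not call itself the ORR denominator; it says whose response is to be classified. On this view the gap is a missing cross-reference. The symptomatic deterioration category in 10.4.4 also suggests that some unassessed patients are meant to be reported, and not as responders. The loss is narrowed further by the early-progression note and by the acceptance of caliper measurement for superficial lesions (10.2.1, 10.3.1).

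Much of this stands. The upward shift is conditional on one reading, and it is small beside the interval. But 10.1.2 is worded as a restriction, it is the only objective-response population, and 11.1 names a set for safety and none for response. The 10.4.4 category covers one of the three groups and does not say whether they stay in the denominator.

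A reader might go further and infer that the stated type I error or power is wrong, either because unevaluable patients would be replaced or because 5% and 20% are rates among evaluable patients only. The documents support neither. No passage provides for replacement, and none describes the design rates as evaluable-only. The rule on 29 is the same before and after the clarification.

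**Conclusion.** The plan should name the denominator of its primary estimate. As written, 10.1.2 can be applied so that treated early failures leave the reported ORR, which then no longer matches the patients behind the decision. With 4 responses the estimate moves from 13.8% to between 14.3% and 17.4% for an assumed 1 to 6 exclusions. The direction is upward whenever there is at least one response. It would be wrong to infer that the bias is always favourable, since 0 responses give 0% on any denominator.

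The go/no-go rule, its type I error of 0.0468 and its power of 0.801 stand, provided 29 are enrolled without replacement. The size rests on assumed exclusion counts and on the assumed 95% exact interval. The loss of patients is possible, not certain. The change is worth making because it is cheap and concerns the primary endpoint, but the design is not at fault.

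**What to change.** State in 10.1.2 and 11.1 that:

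- the primary ORR and its confidence interval use the same 10 and 29 patients as the Simon decisions;
- any of these patients with no post-baseline tumor assessment, including through death, a stop for toxicity or symptomatic deterioration, counts as a non-responder and is not replaced;
- the 10.1.2 evaluable set is used for a supportive analysis only.

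The Simon sizes are written as patients enrolled and can stay so. If any enrolled patient is never treated, report the number and say in advance whether that patient counts toward 10 or 29.

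The cost is a few sentences of protocol wording. The reported ORR may be slightly lower than on the evaluable set. Sample size, decision rule, type I error and power do not change.
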